Hypothesis 1.6 (secondary): Those assigned to placebo will have a higher rate of cotinine-verified, seven-day point-prevalence nicotine vaping abstinence at end of treatment compared to EUC.

Hypothesis 1.7 (exploratory): Those assigned to varenicline will have an earlier onset of abstinence, longer latency to first lapse, longer latency to relapse, longer duration of abstinence, and greater total number of days of vaping abstinence than those assigned to placebo or EUC as

determined by using data ascertained daily with the emocha Mobile Health app (emocha) or REDCap surveys.

Aim 2 (secondary): To establish the safety and tolerability of varenicline in adolescents attempting to quit vaping nicotine.

Hypothesis 2.1: Nicotine withdrawal symptoms, craving, and negative mood symptoms will be less frequent and severe in the varenicline group than the placebo or EUCgroups.

Hypothesis 2.2: Those assigned to varenicline will have no greater incidence or severity of adverse events (AE) compared with those assigned to placebo or EUC during treatment and follow-up.

Aim 3 (exploratory): To assess if there are between group differences in consumption of alcohol, combusted tobacco, cannabis, and non-medical prescription drugs during the treatment and follow-up periods.

Exploratory Hypothesis: Those assigned to varenicline will have less consumption of alcohol, combusted tobacco, cannabis, and non-medical prescription drugs and greater reduction in severity of nicotine dependence as assessed with the ECDI during the treatment and follow-up periods than those in the placebo or EUC groups.

PILOT STUDY 2020P002774-Pilot - NCT04602494

In 2021, during the national recall of varenicline in the US, the FDA provided temporary authorization for importation of apo-varenicline from the Canadian company, Apotex. A pilot vaping cessation trial was conducted using apo-varenicline or identical placebo in 4 study participants who met inclusion and exclusion criteria below except that the age range was limited to 18-25. In this pilot trial, all study procedures listed below were piloted, including the emocha platform for study medication adherence and daily report of vaping behavior and adverse effects and the novel, brief lay-counselor behavioral vaping cessation intervention.

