Eligible participants will be randomly assigned in a 1:1:1 ratio, in blocks of 6, to varenicline, identical appearing placebo prepared by the MGH research pharmacy, or EUC (i.e., TIQ and monitoring with assessments only). Study staff and participants will both be blind to drug for those randomized to the varenicline and placebo arms. Randomization will be stratified by secondary or post-secondary school status. The randomization scheme will be computer generated by the MGH Research Pharmacy by personnel with no other interactions with study staff or participants. There will be separate randomization codes for apo-varenicline, imported from Canada under a provisional FDA allowance, and domestic generic varenicline with full FDA approval. The randomization codes will be held in the MGH research pharmacy, and available to study PIs only in the case of urgent medical need. Assessments will be conducted by study staff who are blind to study intervention. Treatment will be assigned according to study

number, assigned sequentially to eligible participants who enroll in the trial and attend the baseline visit.

Special considerations for individuals living in the same households: More than one household member or family member will be allowed to participate in the study. Since there is a possibility that participants from the same household, voluntarily or not, share study medication, participants from the same household will be yoke randomized, eg assigned to the same intervention. Yoked randomization will ensure members of the same household or family members receive the same intervention and will reduce the risk for contamination.

V. STUDY PROCEDURES

Participants will be randomly assigned to receive a 12-week course of varenicline, an identical placebo, or EUC only. Participants assigned to receive varenicline or identical placebo will receive individual behavioral vaping cessation sessions (held virtually by videoconferencing or in-person), and a digital platform to report vaping behavior, study medication adherence, and tolerability. Participants in EUC will be provided with explicit advice to quit and non-directive support. Participants in all three arms will complete assessments, conducted by raters blinded to study arm assignment, and will include samples for cotinine assays and self-reports of vaping and other drug use. Participants in all three arms will receive an introduction to TIQ and receive weekly monitoring of TIQ use from study staff.

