Before behavioral intervention sessions, participants will fill out assessments of vaping craving and collect saliva for cotinine testing (the latter only occurring if the participant self-reports nicotine abstinence since the last weekly visit). To refine and tailor these interventions to be maximally appealing to and effective for adolescents who vape, we will ask participants for weekly feedback on the appeal, relevance, and effectiveness of the educational topics and skills covered in the program. For participants randomized to the EUC arm, weekly sessions will only consist of non-directive support and assessments noted in the Time and Events Table, including saliva samples for cotinine (collected only to bio-verify self-reported nicotine abstinence).

| Time | Activities |
|--------|---|
| 5 mins | Check-in on adverse events, vaping exposure, and medication adherence |
| 3 mins | New educational content |
| 7 mins | Review of education material and skill/behavior goal |

CBT Structure

Prior to initiating the study intervention, interventionists will complete training conducted by [name] or other doctoral members of study staff on QuitVaping sessions. This will include didactic training on vaping and vaping cessation in adolescents, study methods, theoretical rationale, and background information on the behavioral and pharmacologic interventions. At the end of the training, leaders must achieve a minimum score of 80% on the fidelity scale based on their facilitation of two simulated sessions before they lead a session.

e. Enhanced Usual Care (EUC)

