Neuropsychiatric Adverse Events Interview (NAEI)³⁶ is a semi-structured interview designed to systematically assess the presence and severity of specific neuropsychiatric symptoms and will be administered at enrollment, baseline and at each assessment visits. This instrument will be asked in regards to the past six months (at enrollment) and since the last assessment visit (all other timepoints).

Adverse Events will be assessed weekly by the study staff via REDCap during the treatment phase and then monthly during assessment visits to assess the tolerability of the study procedures.

Concomitant Medications will be assessed by self-report at each visit.

Peer Network Stability: At baseline, V12, and 3-month follow-up, participants will be asked to list and rank up to 10 friends in order of closeness, using a modified version of the "concentric circles of closeness" sociometric measure used in. ^{80, 82} Participants will generate their friends' names by free recall to ensure (1) friends included in the study could come from any context and (2) participants designated only individuals whom they truly considered to be friends.⁸¹ A friendship network instability index will be created by calculating the absolute value of the sum of each peer's rank change divided by the total number of peers the adolescent listed at the consecutive time points to account for differences in network sizes.⁷⁹

Modified Mental Health Youth Satisfaction Survey(YSS)⁶⁹ is a 26-item self-rated survey of youth perception of services in 5 domains: access to services; appropriateness of services; cultural sensitivity; participation; and treatment outcome whose internal consistency ranges from 0.70 - 0.94. It has been widely used in state mental health systems to assess youth satisfaction with services and will be given at week 12 to assess participant satisfaction with the intervention.

The Impulsive Behavior Scale (UPPS-P) – Short⁷⁰ will be given at enrollment to assess five components of impulsivity, including sensation seeking, lack of premeditation, lack of perseverance, negative urgency, and positive urgency. Scores on many of these factors have been shown to relate to risk behavior.

The Wechsler Test of Adult Reading (WTAR)⁷¹ will be used to assess speech and dictation and derive an estimated IQ at enrollment.

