Hypothesis 2.1: We will use a linear model applied separately to repeated, continuous weekly assessments of nicotine withdrawal symptoms, craving, and negative mood symptoms. The linear model will be estimated using generalized estimating equations (GEE), providing estimates and standard errors robust to violations of distributional assumptions (e.g., normality), and heteroscedasticity. The model will be applied to the summed scores at each time point per subject. The analysis will be intent-to-treat with missing data imputed per the method specified above. The key confirmatory effect will be a dummy-coded contrast comparing placebo (coded as 0) against varenicline (coded as 1). Exploratory analyses will also be conducted to evaluate varenicline versus EUC and placebo versus EUC. The model will include covariates for a) change over time (two terms encoding linear and quadratic trends), b) baseline levels of the given outcome, as well as c) sex, environment (secondary school versus post-secondary school), and severity of nicotine dependence. Covariates will be standardized (mean-centered and scaled by the standard deviation). P-values will be adjusted to avoid multiple comparison issues using the Benjamini-Hochberg method.

Hypothesis 2.2: We will conduct a Fisher's exact test differences by randomized group in the number (%) of participants who endorse an AE at least once in the 12-week treatment period. We will evaluate frequent AEs (e.g., that occur in at least 5% of the participants at any point between weeks 1 through 12 of the trial).

Sensitivity analyses: We will conduct 3 sensitivity analyses to examine the robustness of our conclusion for efficacy.

- 1. We will test whether our conclusion on efficacy is robust to the inclusion/exclusion of the 3 covariates (biological sex, environment [secondary school vs. post-secondary school], and nicotine dependence severity) we therefore will rerun the analyses without the 3 covariates and examine whether the pooled estimate for the contrasts between varenicline, placebo, and/or EUC changes in sign and significance.
- 2. We will test whether our conclusion on efficacy is robust to the approach for imputation of missing data, examining whether the pooled estimate for the contrasts between varenicline, placebo, and/or EUC changes in sign and significance.
 - a. We will rerun the adjusted (i.e., with covariates) models on the observed data only.

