All adverse events volunteered, observed, or solicited will be recorded in the AE CRF from the time the subject signs the informed consent up to and including Week 24. The PI will meet weekly with all study investigators to review the details of data acquisition and analysis as well as any minor problems. AEs will be assessed for each subject at every visit. All adverse events will be recorded and will include the dates of occurrence; severity; assessment of relationship to study drug; countermeasure(s); specific drug therapy used in countermeasure; and outcome. Adverse events will be reviewed by the PI who will complete an adverse event report form and submit this to the IRB within the required time frame in accordance with the IRB guidelines.

Reporting Adverse Events: The PI will report all adverse events experienced by the study subjects in accordance with HRC (Human Research Committee) guidelines to the Institutional Review board. Adverse events will also be reported by the principal investigator to the funding agency and to the FDA in accordance with IND regulations. The reporting of adverse events is the responsibility of the PIs, Drs. [name] and [name].

In case of serious adverse events (SAE's), the PI will report them within 24-hours by telephone, fax or email according to HRC guidelines, followed by a written report within 5 business days. SAEs that occur within 30 days after a subject's last dose of study medication that are categorized as definitely, probably or possibly relate¹d to the study will be reported to the HRC and FDA. An annual report will be submitted to the HRC and the FDA of the progress of the trial. This will include individual study information and information on safety reports from the previous year.

X. REFERENCES

- Johnston, L. D. et al. Monitoring the Future National Survey Results on Drug Use, 1975-2018: Overview, Key Findings on Adolescent Drug Use. (Institute for Social Research, 2019).
- Wang, T. W. *et al.* Tobacco Product Use and Associated Factors Among Middle and High School Students — United States, 2019. *MMWR Surveill. Summ.* 68, 1–22 (2019).
- 3. Barrington-Trimis, J. L. & Leventhal, A. M. Adolescents' Use of 'Pod Mod' E-Cigarettes Urgent Concerns. *The New England journal of medicine* **379**, 1099–1102 (2018).
- 4. Kong, G. & Krishnan-Sarin, S. A call to end the epidemic of adolescent E-cigarette use. *Drug and Alcohol Dependence* **174**, 215–221 (2017).

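### Only the two tablet arms have a digital tolerability report, so the Hypothesis 2.2 comparison of varenicline with EUC may pick up unequal adverse event capture unless the plan fixes the source of events

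*Combined protocol and SAP*

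**What the plan says.** **Capture in the tablet arms.** The opening paragraph of Section V lists, for varenicline and placebo participants, behavioral sessions and "a digital platform to report vaping behavior, study medication adherence, and tolerability". The pilot paragraph in Section II describes the same system as "the emocha platform for study medication adherence and daily report of vaping behavior and adverse effects". The Study Compensation section pays up to $168 for app and survey completion in these arms and $0 in EUC. The CBT Structure table in Section V.d opens each session with "Check-in on adverse events, vaping exposure, and medication adherence".

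**Capture in EUC.** "Participants in EUC will be provided with explicit advice to quit and non-directive support". Section V.d limits the weekly EUC contact to that support and the scheduled assessments. No digital platform is listed.

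**Capture in all arms.** Under Section V.f, AEs "will be assessed weekly by the study staff via REDCap during the treatment phase", then monthly. The Time and Events Table has one AE row covering every visit from baseline, with no restriction by arm. The NAEI is given to everyone at weeks 4, 8 and 12 of treatment.

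**Recording and analysis.** Section IX.d states: "All adverse events volunteered, observed, or solicited will be recorded in the AE CRF". Hypothesis 2.2 in Section II predicts no excess of AEs on varenicline over placebo or EUC. Section VI tests it with Fisher's exact test across the randomized groups on the "number (%) of participants who endorse an AE at least once in the 12-week treatment period", and looks at individual AEs that reach 5%. It does not say which reports count.

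**The concern.** The endpoint is whether a person ever reported an AE. Such an endpoint depends on how many routes there are for reporting as well as on how many events occur. Two arms have a route that the third lacks, all routes lead to one form, and the analysis does not choose among them.

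At stake is the varenicline-EUC half of Hypothesis 2.2. Extra capture on varenicline works against the trial's own prediction and would look like drug harm. Section VI itself says that medication in this age group must justify its risk, so a spurious excess over usual care would matter to readers. The same would apply to a placebo-EUC contrast, if one is run.

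**Working it through.** The plan states no AE rate, power or capture figure, so there is none to reproduce. The direction comes from the text. The size can only be illustrated.

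**1. Reporting routes over 12 weeks**

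| Route | Varenicline, placebo | EUC |
|---|---|---|
| Weekly staff AE query | 12 | 12 |
| NAEI, weeks 4, 8, 12 | 3 | 3 |
| Digital tolerability report | yes; 12 × 7 = 84 if daily | none |
| Check-in at counselling session | at the weekly contact | none listed |

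The payment cap fits 84 days of app use: $168 / $2 per day = 84. It does not show that each day includes an AE question. The counselling check-in falls at the same weekly contact as the common query and may simply be that query, so I count only the platform as extra capture.

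**2. Direction.** Let p be the proportion with an AE recorded through the common instruments, and k the share of the remaining participants for whom the platform alone adds one. The recorded proportion is p in EUC and p + k(1 − p) in a tablet arm. For any k above 0 the tablet arm is higher, with no true difference.

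**3. Size, illustrated.** The arm size is 240 / 3 = 80, from the maximum randomized and the 1:1:1 ratio. The two-sided 0.05 level, p and k are assumptions. The result is the exact rejection probability of Fisher's test, found by enumerating all tables.

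With p = 0.50:

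| k | Tablet arm | EUC | P(reject) |
|---|---|---|---|
| 0 | 0.50 | 0.50 | 0.032 |
| 0.10 | 0.50 + 0.10 × 0.50 = 0.55 | 0.50 | 0.069 |
| 0.25 | 0.50 + 0.25 × 0.50 = 0.625 | 0.50 | 0.291 |
| 0.40 | 0.50 + 0.40 × 0.50 = 0.70 | 0.50 | 0.677 |

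With the same three non-zero values of k, p = 0.20 gives 0.171, 0.745 and 0.987, and p = 0.80 gives 0.041, 0.094 and 0.216.

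**4. A second model.** Give both arms the same true incidence, and let each existing case be detected with probability 0.9 in the tablet arm and a lower probability in EUC.

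| True incidence | 0.9 v 0.9 | 0.9 v 0.8 | 0.9 v 0.7 | 0.9 v 0.5 |
|---|---|---|---|---|
| 20% | 0.031 | 0.040 | 0.072 | 0.238 |
| 40% | 0.034 | 0.061 | 0.150 | 0.552 |
| 60% | 0.032 | 0.086 | 0.268 | 0.832 |

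In both models, most rejections under unequal capture show more AEs in the tablet arm, and nearly all do once the gap is more than slight. The effect ranges from negligible to large, depending on inputs that the documents do not supply.

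**The case against.** The best defence is that the plan already uses a common source. Section V.f is where the AE measure is defined, and it names the weekly staff query, which every arm receives. The word endorse in the Hypothesis 2.2 analysis suits a structured query. Section IX.d concerns recording and reporting, and does not define an analysis set. This reading is possible, but Section VI does not adopt it, and a data set built from the AE form would include platform reports. The bias is therefore something that could happen, not something that must.

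Three stronger readings are tempting and go beyond the documents.

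- *The main trial asks about AEs daily.* Only the pilot text says so: "daily report of vaping behavior and adverse effects". That paragraph does say that the procedures set out below it were piloted. In the main-trial text, Section V mentions tolerability without a frequency, and the daily row of the Time and Events Table covers vaping yes/no only.
- *Counselling sessions are a second unequal source.* They share the weekly contact with the common query, so additional capture is not shown.
- *A placebo-EUC AE test is planned.* Hypothesis 2.2 names varenicline against placebo or EUC. A placebo-EUC contrast enters only if the reference to randomized groups is read as all pairs.

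It is also true that an extra prompt matters only for someone who reports no AE at any of about 12 weekly queries, so the larger values of k would need justification. Aim 2 is secondary, and the stopping criterion compares the active arm with placebo, where capture is equal.

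**Conclusion.** The concern holds as a conditional one. The tablet arms have a tolerability report that EUC lacks, one form takes events from all sources, and the analysis does not restrict the source. If platform reports are counted, the varenicline-EUC comparison is biased towards more AEs on varenicline. Varenicline versus placebo is not affected.

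The direction follows from the text, but the size does not. With 80 per arm and an assumed 50% base, false rejection is 7% to 68% for k from 0.10 to 0.40, against 3% with equal capture. Other assumed inputs give anything from 4% to 99%. These figures show that the issue can matter. They are not estimates for this trial. The point should be settled before analysis, because it concerns a secondary aim, the direction is clear, and the remedy is cheap.

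**What to change.** 1. In Section VI, Hypothesis 2.2, define any comparison with EUC on AEs endorsed at the instruments given on the same schedule in all three arms: the weekly study-staff AE query at weeks 1-12 and the monthly NAEI. Count an event whenever it is endorsed there, even if it was also, or earlier, reported on the app.
2. Add a source-of-report field to the AE form that allows more than one source per event.
3. Report AEs captured only by the app in a separate table, for varenicline versus placebo only.
4. State which pairs of arms are tested.

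The counting rule in item 1 matters. Assigning each event to the source that caught it first would drop tablet-arm events logged on the app and then repeated at the weekly query, while the same events counted in EUC. For illustration, if true rates are 50% and a quarter of tablet-arm reporters are lost that way, 0.50 × 0.75 = 0.375 is compared with 0.50. Fisher's test at 80 per arm then rejects in 29% of trials, this time in favour of varenicline.

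All events still go to safety reporting and the DSMB. The cost is one form field and a few sentences in the plan. The small downside is that AEs reported only on the app leave the EUC comparison. The change equalizes the instruments, but it cannot remove any effect of app prompting on what participants recall at the weekly query.

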Note: No IND was sought to enroll children into the trial with the apo-varenicline study medication, as it was being used under temporary FDA authorization. When US-made, generic varenicline was FDA approved (August 2021) and available for purchase through PAR Pharmaceuticals (November 2021), an IND was sought (December 2021) to enroll children ages 16 and 17 into the trial. This trial was deemed exempt in March 2022. When IND exemption was granted for enrolling children ages 16 and 17, IRB approval was sought for the main trial which will uses generic US made varenicline in participants ages 16-25.

III. SUBJECT SELECTION

a. Inclusion/exclusion criteria

Inclusion Criteria:

- Ages 16-25, inclusive;
- Self-report of daily or near daily nicotine vaping for the prior \geq 3 months and semiquantitative saliva screening for cotinine positive for recent nicotine use;
- Nicotine dependence as defined by a score ≥4 on the 10-item E-cigarette Dependence Inventory (ECDI), or report of persistent use despite negative consequences, or prior failed quit attempts;

- Self-report of no regular combusted tobacco use in the past 2 months at enrollment and exhaled CO <10 ppm;
- Total body weight at enrollment \geq 35 kg (77 lbs);
- Report willingness to try varenicline to stop vaping;
- Able to understand study procedures and read and write in English;
- Have a parent or legal guardian who is able and willing to provide written informed consent (if under the age of 18);
- Competent and willing to provide written informed consent (if age 18+) or assent (if under 18);
- For participants who could become pregnant: negative urine pregnancy test at enrollment and agreement to use effective contraception (e.g., abstinence, hormonal contraception, intra-uterine device, sterilization, or double barrier contraception) during the study.

Exclusion Criteria:

- Use of a smoking cessation medication in the prior month (nicotine patch, gum, nasal spray, or inhaler, varenicline, bupropion);
- Unwilling to abstain during the study from using smoking cessation aids other than those provided by the study;
- Unstable medical condition, epilepsy, severe renal impairment;
- Inpatient psychiatric hospitalization in the prior 6 months, serious suicidal ideation or suicide attempt within 6 months of enrollment, recent active suicidal ideation or suicidal behavior identified at enrollment or baseline visits;

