This assessment includes general demographic items and basic questions related to health behavior and psychological functioning. All students who are not withdrawn from the schoolwide assessment by their parents/guardians and who wish to complete the questionnaire will also complete a separate form where they may provide their contact information and indicate their interest in being contacted for research studies. Questionnaires will be reviewed by MGH study staff, and all students who meet the criteria to participate in the study based on this initial screening and who provided contact information will be contacted by MGH study staff to conduct a telephone screener or will be provided a link to complete the screener as a REDCap survey. The telephone screener will involve an explanation of study procedures as well as questions to screen for eligibility for the trial.

Students who express interest in participating in the study and are eligible based on the telephone screen will be scheduled for an in-person or virtual enrollment visit to sign consent (assent if under the age of 18) and complete eligibility screening procedures. A member of study staff will conduct informed consent procedures with at least one parent/guardian of participants under the age of 18 either in-person or via telephone/zoom prior to initiating study procedures. Parents/guardians will have the option to sign the ICF electronically if that is their preference.

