a. Study visits and parameters to be measured

The enrollment visit will be conducted in person and will include a detailed description of the study, informed consent/assent, assessments to confirm eligibility, assessments of vaping and other drug use behavior, and medical and psychiatric diagnostic and symptom assessments. Eligible, consented participants will then be scheduled for a baseline assessment visit where they will receive study medications (for those randomized to varenicline or placebo arms), weekly visits which will include assessments (all participants) as well as the behavioral vaping cessation sessions (for those randomized to varenicline or placebo arms), and monthly assessment visits. Following completion of the 12-week intervention period, participants will be scheduled for follow-up visits at weeks 16, 20, and 24. Study visits will be conducted at our MGB location, or in a private room at a participant's local library or current school. When conducting a study visit at a site external to MGH, study staff will obtain verbal permission from library/school administrators to conduct study visits at a given location. When obtaining permission to conduct a visit, no identifying or specific information regarding the participant or the study will be mentioned. All study visits can be conducted in person or virtually. We have piloted procedures and have a standard operating procedure for sending materials to conduct urine drug and pregnancy screening during virtual visits. Study staff will include instructions for participants to perform the tests and hold the assays up to their device's camera so study staff can record urine screening results. Height and weight will be recorded per participant's report for remote visits. Carbon monoxide will not be recorded for virtual visits, and we will rely on participant reported combusted tobacco use. Medication will be shipped via priority mail if a visit where medication is distributed is done virtually. Blood pressure and heart rate will not be collected if a visit is virtual, as these are not necessary measures in prescribing varenicline or part of our primary outcomes.

Time and Events Table

Time and Events

| | | | Follow-up period | | | | | | | | |
|--|------------|-------------|------------------|---------|-----------|---------|------------|----------|----------|----------|----------|

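### The plan conflicts on whether enrollment may be virtual; if it may, an unverified self-reported weight sets the dose for 16–17-year-olds, and the exhaled-CO half of an entry criterion goes unassessed (minor)

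*Combined protocol and SAP*

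**What the plan says.** **Visit mode.** Section IV.a says, for both the school-based and the non-school-based route, that likely eligible people are "scheduled for an in-person or virtual enrollment visit to sign consent" and to complete eligibility screening. Section V.a opens with "The enrollment visit will be conducted in person and will include a detailed description of the study", and later in the same paragraph says "All study visits can be conducted in person or virtually", with no exception for enrollment. The COVID-19 Design Consideration also allows both modes.

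**Exhaled CO.** The inclusion criterion in Section III.a reads "Self-report of no regular combusted tobacco use in the past 2 months at enrollment and exhaled CO <10 ppm". Section V.f (Measures of smoking abstinence) places the CO measurement at enrollment, and the Time and Events Table marks it there and nowhere else. Section V.a adds that "Carbon monoxide will not be recorded for virtual visits, and we will rely on participant reported combusted tobacco use".

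**Weight and dose.** The Time and Events Table schedules height and weight at enrollment only. Section V.a says "Height and weight will be recorded per participant's report for remote visits" and "Medication will be shipped via priority mail if a visit where medication is distributed is done virtually". Section V.b sets the dose for ages 16–17 by a 55 kg cut-off and gives everyone aged 18 or over the higher schedule whatever their weight. Section VI (Statistical Design and Power) instead says that dosing goes by weight rather than age.

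**The concern.** Staff at the site have two instructions about how a participant may enroll, and nothing that says which one governs. If the in-person sentence governs, nothing further follows. If virtual enrollment is allowed, two things do.

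First, dosing. The only scheduled weight becomes a figure that the participant supplies, and for a minor on varenicline that figure selects one of two schedules that differ about two-fold. The baseline visit may also be remote with drug sent by mail, so the plan requires no verified weight before the first dose. The same self-report settles the 35 kg entry minimum. Section V.a justifies omitting blood pressure and heart rate remotely on the ground that prescribing does not need them. That reason cannot cover weight, because the 16–17-year-old dose does need it.

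Second, eligibility. The entry criterion joins self-report and CO with an *and*. For a virtual enrollee the CO half cannot be documented, so each such enrollment raises the question of whether it is a deviation.

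**Working it through.** **1. Visit mode, side by side**

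| Place | Enrollment mode |
|---|---|
| IV.a, school-based route | in person or virtual |
| IV.a, non-school-based route | in person or virtual |
| V.a, opening sentence | in person |
| V.a, later in the same paragraph | any visit, either mode |
| COVID-19 Design Consideration | either mode |

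The conflict lies between IV.a and V.a and also within V.a. All of this is current text.

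**2. CO.** CO has one scheduled time point, enrollment. The V.a sentence on virtual visits can therefore only refer to a virtual enrollment visit. It supplies a fallback, self-report. Sections III.a and V.f contain no matching exception. The criterion is then unassessed for a virtual enrollee; it is not failed.

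**3. Scheduled dose for ages 16–17 (V.b schedule, 84 days)**

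- 55 kg or less: 0.5 × 7 + 1.0 × 77 = 80.5 mg.
- Over 55 kg: 0.5 × 3 + 1.0 × 4 + 2.0 × 77 = 159.5 mg.
- Ratio: 159.5 / 80.5 = 1.98.
- Baseline two-week supply: 0.5 × 7 + 1.0 × 7 = 10.5 mg, against 0.5 × 3 + 1.0 × 4 + 2.0 × 7 = 19.5 mg. The first dispensing therefore already carries the difference.

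**4. How many could be misdosed.** Only remotely enrolled 16–17-year-olds on varenicline who misreport across 55 kg, in either direction, are affected. The varenicline arm is up to 240 / 3 = 80. The documents give none of the other shares, so these are assumptions: 10–40% aged 16–17, 0–50% enrolled virtually, 2–10% misreporting across 55 kg.

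Number = 80 × age share × virtual share × misreporting share

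- No virtual enrollment: 0.
- Middle: 80 × 0.25 × 0.30 × 0.05 = 0.3.
- Top: 80 × 0.40 × 0.50 × 0.10 = 1.6, which is 1.6 / 80 = 2% of the arm.

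If the weight-based rule in Section VI governs, the age share drops out. With the same assumed shares for adults, the middle is 80 × 0.30 × 0.05 = 1.2 and the top is 80 × 0.50 × 0.10 = 4.0.

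**5. How many could enter without CO.** 240 × virtual share: 240 × 0 = 0 up to 240 × 0.50 = 120 of up to 240 randomized, on the same assumed range.

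**The case against.** The best defense is that V.a already settles the CO question. Since CO is taken only at enrollment, its sentence on virtual visits must be a deliberate fallback. That stands: a reader might infer that the plan has no rule for these participants, or that they fail the criterion, and the text supports neither. What remains is that the eligibility list and Section V.f were not brought into line.

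A reader might also infer that smokers could enter unchecked and distort the result. The documents do not support this. Virtual enrollees must still report no regular smoking. Urine NNAL is assayed at baseline, Section V.f calls it the more sensitive check, and the protocol describes home specimen collection. NNAL is not an entry criterion, so it does not replace CO, but it is a later biochemical check. Smoking status at entry also precedes randomization and should be balanced between arms in expectation.

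On dose, the inference that light minors will be overdosed goes too far. Section VI offers 1 mg twice daily only to those who tolerate 0.5 mg twice daily, and Sections V.b and VII.i allow reduction. Section VII.i cites a 307-person adolescent trial reporting no tolerability difference by dose, although Section VI notes numerically more nausea, vomiting and headache at the high dose. These points reduce the concern without removing it. The V.b schedule has no tolerability step before 1 mg twice daily, dose reduction acts only after symptoms, and neither safeguard corrects an under-dose from an under-reported weight.

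Lastly, restricting the concern to ages 16–17 follows V.b. Section VI would extend it to adults, so the restriction is the conservative reading.

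**Conclusion.** The inconsistency is real, and its consequences depend on virtual enrollment being permitted. In that case an unverified weight chooses between two schedules about two-fold apart for a 16–17-year-old, and the CO half of the smoking criterion is replaced by self-report without the eligibility text saying so.

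The size is small. The number misdosed runs from 0 to about 1.6 following V.b, and the range rests entirely on assumed age, virtual and misreporting shares. A dose error would act in the varenicline arm only, but at 2% of that arm or less (5% at the top of the range, 4.0 / 80, if Section VI governs) it is not expected to bias the primary contrast materially. Severity: minor. It is worth correcting because the input concerns a minor's dose and the check costs very little.

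**What to change.** 1. **State one enrollment mode** in Sections IV.a and V.a. If it is in person only, the other two changes are unnecessary.
2. **If virtual enrollment is kept, verify weight.** Before assigning the dose and sending the first supply to any remotely enrolled 16–17-year-old, have staff view a scale reading by video or weigh the participant in person. Section V.a already has participants "hold the assays up to their device's camera so study staff can record urine screening results", so the method is in place. If the Section VI dosing rule governs, apply this to everyone whose dose depends on weight.
3. **Carry the CO exception into Sections III.a and V.f**: CO below 10 ppm if enrolled in person; self-report if enrolled virtually. Report how many entered without CO, with their baseline NNAL.

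The cost is protocol wording and one observed scale reading per affected participant. A few will need access to a scale or a short visit. Non-smoking at entry will rest on self-report for virtual enrollees until the baseline NNAL result is available. No new assay is needed, and the only added reporting is a descriptive count.
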